Our hypotheses were formulated in line with PICOS (Population-Intervention-Comparison-Outcome-Study); significance was set at 0.05 (Higgins et al., 2019). In addition to standard applications, the intervention group will be using the PREDIABE-T^R mobile app. The control group will only use standard applications. In this context, our research hypotheses are the following:

H1a: When compared with the control group, the eating behaviors with regard to adopting the Mediterranean Diet of prediabetic adults using the PREDIABE-T^R app will be at a higher level.

H1b: When compared with the control group, the physical activity (MET, number of steps) of prediabetic adults using the PREDIABE-T^R app will be at a higher level.

H1c: When compared with the control group, the metabolic parameters (A1C, Impaired Fasting Glucose-IFG, Impaired Glucose Tolerance-IGT) of prediabetic adults using the PREDIABE-T^R app will be at lower levels.

H1d: When compared with the control group, prediabetic adults using the PREDIABE-T^R app will lose more weight.

METHODS

Study design

This study protocol was drawn up for a single center, single-blind (participant), pretest-posttest, follow-up, parallel group (1:1 ratio) randomized controlled trial (Fig.1). The study protocol was prepared on the basis of the following Standard Protocol Items: Recommendations for Interventional Trials (SPIRIT) guidelines (Chan et al., 2013) and the Consolidated Standards of Reporting Trials, Non-Pharmacological Treatment Interventions Checklist (CONSORT-NPT) (Boutron et al., 2017). The study was registered on ClinicalTrials.gov on XXX with the ID XXXX.

Study setting and population

This study will be carried out at the Yıldırım Beyazıt Family Health Center (FHC) No. 9, a facility in the city of Kutahya, in western Türkiye. No. 9 is an FHC that addresses a large city population and where 5 physicians and 5 midwives work. The target sample will consist of prediabetic adults. The study will be conducted in the FHC between January and July 2023.

Sample size determination

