The study universe will consist of adults of the ages 45-65 who have received a diagnosis of prediabetes and are registered at the Kütahya FHC No. 9. The sample size determined by power analysis is based on calculations made with the G-Power program that were used in a similar study. Effect size is 0.666 (Chen et al., 2015, Everett et al., 2018); level of significance, 0.05; confidence interval limit 95%; testing power, 90%. The optimal number of participants calculated in the two-way hypothesis review was found to be 49 for each group. In previous studies (Chen et al., 2015; Zhang et al., 2017), the size was increased by 10% to allow for losses. Ultimately, the decision was to enroll 60 participants in each group.

Inclusion criteria

- Individuals to be included will be those who: are prediabetic (Impaired Fasting Glucose-IFG=100-125 mg/dl-mmol/L, A1C=5.7%-6.4% or Impaired Glucose Tolerance-IGT=140-190 mg/dl-mmol/L),
- are active Android/IOS cell phone users,
- are not pregnant or have any malignancy,
- have no hearing or vision impairment,
- are at least primary school graduates and fluent in Turkish.

Exclusion criteria

- Individuals who have a diagnosis of diabetes or are using an insulin pump or oral antidiabetic agents,
- have vision impairment,

[figure not shown]
- are pregnant,
- have any condition that precludes engaging in physical activity,
- have psychiatric issues or problems with communicating, will be excluded.

Randomization

The stratified block randomization (1:1) will be used to attain objectivity in assigning individuals to the experimental group that will be using the mobile app and to the controls who will be following routine practices (Brugnara et al., 2016; Kautzky-Willer et al., 2016; Kautzky-Willer et al., 2019). The variable “**gender**” will be used as the control variable in the stratified block randomization.

Blinding and Preventing Bias

The researchers cannot be blinded in this study since they were the parties to develop the application and will be involved in the training. On the other hand, the participants can be blinded because they are to be using either the PREDIABE-T^R app or the Türkiye Nutrition Guide. In order to prevent bias, the collection of the randomized assignment data will be handled by a researcher who is not actively involved in the study; this researcher will submit the data in opaque envelopes to the implementing researcher.

Intervention Group

PREDIABE-T^R mobile app group

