Users can enter the foods they eat into the application and are informed of the benefit/harm of these foods with a red/green light alert. The weight-to-height risk table of the Turkish Diabetes Foundation has been added to the BMI section, where additionally, individuals can automatically calculate their BMI according to the entered height and weight data (<https://www.turkdiab.org/diyabet-hakkinda-hersey.asp?lang=TR&id=59>, Access Date: 9 January 2022). Furthermore, this section will also provide users with 14 recommendations from the Mediterranean Diet Adherence Screener-MEDAS.

Physical Activity

Physical activity will be followed up with a step-count and a scheduling of the recommended physical activity the participant should engage in during the week. A gold star icon will be sent to app users when they satisfy their physical activity requirement. At the end of the study, those who have collected 18 or more gold stars will be gifted bracelets inscribed with "Keep Active, Keep Protected from Diabetes!"

Communications

This module will allow users to send direct messages to the researcher, 24/7 for any information they may need.

Notifications

This section contains information based on the guidelines of the International Diabetes Federation (IDF), the American Diabetes Association (ADA), the Turkish Ministry of Health, Association of Turkish Dieticians, the Turkish Diabetes Foundation, Turkish Diabetes Society, and the Turkish Diabetes Nursing Association on the signs and symptoms of diabetes and prediabetes, diagnosis, treatment, complications, nutrition, physical activity, BMI monitoring and the normal BMI range. The section is designed to inform users about the content of the guidelines and raise awareness and knowledge levels about diabetes.

Safety

This section contains the data and passwords users will use to access the system.

Active Control Group

Besides the routine health monitoring of the active controls, this group will be instructed in how to download and use the Ministry of Health's Türkiye Nutrition Guide Mobile Application.

Brochures of the Public Health Directorate on healthy nutrition, physical activity, chronic illnesses, and screening.

Data Collection

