Data will be collected on the individuals' sociodemographic features, gender, age, education, profession and medications they are taking. Their diabetes risk will be measured by means of the Finnish Diabetes Type-2 Risk Score (FINDRISK). The data collection form will be filled out on the basis of self-reporting. FINDRISK was developed in 1987 by Tuomilehto and Lindström to identify individuals at risk of Type-2 diabetes mellitus without laboratory testing (Lindström et al., 2003). The Turkish validity and reliability study for FINDRISK was performed by Etbaş Demirağ in 2016 (Etbaş Demirağ, 2016). The participants' metabolic measurements will be taken by a researcher using the

Accu-Chek® Performa Nano device from a capillary blood sample; A1C values will be retrieved from FHC records.

Outcome criteria

The expected primary outcome is a change in the adherence to the Mediterranean diet, physical activity levels and in the prediabetes metabolic values of the adults. The secondary outcome is a change in the adults' ability to achieve weight loss.

Primary outcome criterion

Mediterranean Diet Adherence Screener-MEDAS)

The Turkish validity and reliability studies for MEDAS, which was originally developed in 2012 by Martínez-González et al., were performed by Özkan Pehlivanoglu et al. in 2020 (Martínez-González et al., 2008; Özkan Pehlivanoglu et al., 2020). MEDAS consists of 14 questions (León-Muñoz et al., 2012). Each question is worth 1 or 0 points, depending on consumption. A total score of 7 or above indicates that the individual is adhering to the Mediterranean diet at an acceptable rate; a score of 9 or above indicates strict adherence. Cronbach's alpha coefficient for the scale is reported to be 0.829.

International Physical Activity Questionnaire (IPAQ)

The IPAQ International Physical Activity Questionnaire-Short Form was developed in 1996 by Booth in order to identify the risk factors of inactivity and physical activity levels in prediabetes. The Turkish version of the IPAQ-Short Form consisting of 7 questions will be used. The Turkish validity and reliability studies for this questionnaire were conducted by Saglam et al. (Öztürk, 2005; Saglam et al., 2010).

Metabolic Measurements

The participants' A1C, fasting blood glucose-postprandial blood glucose (whichever is appropriate for the individual) values will be measured.

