The **A1C Measurement** represents a 3-month mean value (Block et al., 2015; McLeod et al., 2020; Toro-Ramos et al., 2020). The A1C testing does not require fasting conditions. The blood sample can be taken at any time of day (TEMDD, Diabetes Mellitus Complications Diagnosis, Treatment and Monitoring Guidelines, 2018). Over the period

of the study, the A1C result the participant has obtained from being tested at any health facility will be taken from the personal health system records.

Blood Glucose Measurement: The researcher will measure the participants' blood glucose with a Roche Accu-Chek® Performa Nano device (www.rochediagnostics.com.tr, Access Date: 4 May 2022). A minimum eight-hour fasting period will be taken as a criterion for fasting blood glucose (ADA, 2020); a postprandial blood glucose test will be administered 2 hours after a meal.

Secondary outcome criterion

Height-Weight Measurement and Body Mass Index

The researcher will measure the individuals' height and weight with calibrated devices. BMI will be calculated with the formula: weight (kg)/height (m²) (TEMED, Obesity Diagnosis and Treatment Guidelines, 2019).

Mobile App Usability and Usage Assessment Scale

Three measures developed by Hoehle et al. (2016) to assess the usability and usage of a mobile application will be used. The validity and reliability study for the scales was performed by Güler (2019).

Mobile Application Usability Scale-MAUS

This is a measure used to assess and understand how the mobile app can be improved and how it may be made more user-friendly. The scale is a 7-point Likert-type and has a total of 40 items (1=Definitely disagree, 7=Completely agree). Cronbach's alpha coefficient for the scale is reported as 0.80-0.94 (Güler, 2019).

Continued Intention to Use Scale-CITUS

This measure was developed to assess how eager individuals are to use the app. It comprises a total of 6 items and is a 7-point Likert-type (1=Definitely disagree, 7=Completely agree). There are no reversely scored items on the scale. Cronbach's alpha coefficient for the scale is reported as 0.90 (Güler, 2019).

Brand Loyalty Scale-BLS

This scale was developed to determine the extent of individuals' loyalty to the mobile app. It comprises a total of 5 items and is a 7-point Likert-type (1=Definitely disagree, 7=Completely agree). There are no reversely scored items on the scale. Cronbach's alpha coefficient for the scale is reported as 0.86 (Güler, 2019).

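### Post-meal glucose is read 2 hours after an unspecified, unrecorded meal in a trial of a dietary app, so a lower 6-month value cannot be read as better glucose tolerance

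*Combined protocol and SAP*

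**What the plan says.** - **Test procedure (Blood Glucose Measurement).** The fasting reading has a defined condition: "A minimum eight-hour fasting period will be taken as a criterion for fasting blood glucose". For the other reading only the interval is set: "a postprandial blood glucose test will be administered 2 hours after a meal".
- **Who gets which test (Metabolic Measurements).** "fasting blood glucose-postprandial blood glucose (whichever is appropriate for the individual) values will be measured".
- **Hypothesis H1c.** Lower values are predicted in app users than in controls for "the metabolic parameters (A1C, Impaired Fasting Glucose-IFG, Impaired Glucose Tolerance-IGT".
- **Entry (Inclusion criteria).** One of the alternative qualifying bands is "Impaired Glucose Tolerance-IGT=140-190 mg/dl-mmol/L", with no test procedure given.
- **Status of the outcome (Outcome criteria).** The primary outcome is a change in Mediterranean diet adherence, "physical activity levels and in the prediabetes metabolic values of the adults".
- **What the app does (Module 3, Nutrition).** Users can log what they eat and get a colour-coded verdict on each food. The same section gives users the 14 MEDAS recommendations, and the description of the intervention adds weekly healthy-eating messages.
- **What controls receive (Active Control Group).** The Ministry of Health nutrition guide app, with public-health brochures that cover healthy nutrition.

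No section sets the content, size or time of the pre-test meal, asks for it to be recorded, or matches it between visits. Data Analysis names ANCOVA but plans no adjustment for it.

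**The concern.** A 2-hour post-meal reading depends on how the person handles glucose and on what was eaten. In many trials a free choice of meal only adds noise. Here one arm uses a tool meant to change food choice, and H1a predicts that the arms will differ in diet. The pre-test meal may therefore differ by arm for reasons that come from the allocation itself.

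H1c is worded as a claim about metabolic state and names glucose tolerance. The Conclusion says that reductions in metabolic parameters would allow the app to be called effective and that policy-makers would be told. If post-meal values feed that judgement, a different meal on the test day could pass for a metabolic gain. Since the plan does not collect what was eaten, the analysis could not separate the two afterwards. The app's food log would not fill the gap: entering foods is optional, and controls do not have it.

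**Working it through.** **1. The sections side by side.**

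| Element | Fasting glucose | Post-meal glucose |
|---|---|---|
| Condition before the test | at least 8 hours without food | 2 hours after any meal |
| Meal content or amount | not applicable | not stated |
| Meal recorded or matched across visits | not applicable | not stated |
| Name in H1c and entry | impaired fasting glucose | impaired glucose tolerance |

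The measured quantity and the named quantity agree in the first column and not in the second.

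**2. Why randomisation and baseline adjustment do not help.** As a simple additive model, let the 6-month reading be

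Y = tolerance part + meal part + error.

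The expected difference between arms is

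E(Y, app) − E(Y, control) = difference in tolerance + difference in pre-test meal effect.

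Randomisation makes the expected meal effect equal at baseline. The 6-month meal comes after allocation and can be influenced by it, so its difference need not be zero. Baseline ANCOVA subtracts a multiple of the baseline difference, which is zero in expectation, and leaves the meal term in place. Giving each person the same type of test at both visits does not remove it either.

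**3. The plan's own figure.** Sample size determination gives effect size 0.666, two-sided alpha 0.05 and power 90%.

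n = 2 × (1.960 + 1.282)² / 0.666² = 47.4, so 48 per group; the exact t-test solution is 48.36, so 49, as stated.

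The figure reproduces. It contains no standard deviation for post-meal glucose and is not tied to that outcome, so it does not help to size the problem.

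**4. Illustration only.** The documents give no SD for post-meal glucose, no meal effect and no number tested post-meal. All three are assumed here: SD 25 or 35 mg/dl; a meal-only difference between arms of 5, 10 or 15 mg/dl; 15, 30 or 60 per arm. With d = difference / SD and no change in tolerance, the probability of a significant two-sided t test at 0.05 is:

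| Tested per arm | SD | 5 mg/dl | 10 mg/dl | 15 mg/dl |
|---|---|---|---|---|
| 15 | 25 | 0.08 | 0.19 | 0.36 |
| 15 | 35 | 0.07 | 0.12 | 0.21 |
| 30 | 25 | 0.12 | 0.33 | 0.63 |
| 30 | 35 | 0.09 | 0.19 | 0.37 |
| 60 | 25 | 0.19 | 0.58 | 0.90 |
| 60 | 35 | 0.12 | 0.34 | 0.64 |

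The last two rows assume that everyone is tested post-meal. With no difference in meals the probability is 0.05 throughout. The spread from 0.07 to 0.90 shows how little the documents pin down.

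**The case against.** **Eating differently is the treatment.** If app users habitually choose other meals, lower glucose after their usual meal is a real consequence of the app, and the procedure section does call the test postprandial glucose. This stands: glucose after a usual meal is a legitimate outcome. It is not the one H1c names. Dietary change is already measured by MEDAS under H1a, and the plan does not say that the pre-test meal must be a usual one.

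**The control arm also gets dietary advice.** This stands too. Only the between-arm difference in the pre-test meal matters, and it may be small. A reader might infer that the arms will arrive after systematically different meals and that the bias can run only towards the app. The documents do not establish either. They do not say that following the MEDAS recommendations lowers the glucose load of a single meal, and the app also targets physical activity.

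**A large false-positive rate might be inferred from the entry bands.** Subtracting the band midpoints gives 165 − 112.5 = 52.5 mg/dl. Calling the app arm's meal 10% to 20% lighter gives shifts of 5.25 to 10.5 mg/dl. A uniform SD of 50/√12 = 14.4 and 25 per arm then give rejection rates of 24% to 71%. The arithmetic is right, but the inputs are not the plan's. The bands are alternative entry routes, so their difference is not a within-person rise. Nothing confines 6-month values to 140-190. The meal reduction and the 25 per arm are invented. The same shifts give 7% to 14% with SD 25 and 10 per arm, and 8% to 18% with SD 35 and 25 per arm.

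**Scope is limited.** Fasting glucose and A1C do not depend on the pre-test meal, H1c does not name post-meal glucose, and no rule lets that reading decide H1c alone. This limits the consequence but leaves the mismatch between test and hypothesis.

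**Conclusion.** The point holds in a limited form. The post-meal reading is taken after a meal that is neither fixed nor recorded, in a trial whose intervention acts on food choice. A lower 6-month value in the app arm can therefore reflect the meal and cannot be read as better glucose tolerance. One would expect any bias to favour the app, but its direction and size cannot be computed from the documents.

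The conclusion rests on two things: that post-meal glucose is the reading meant to stand for the tolerance component of H1c, which is an inference from Hypotheses and Metabolic Measurements read together; and that pre-test meals may differ by arm, which is plausible from the app's design but not shown. It reaches only participants given the post-meal test, whose number is not stated. The plan should be changed before data collection, because unrecorded meals cannot be recovered later.

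**What to change.** 1. In Metabolic Measurements and Blood Glucose Measurement, take the 8-hour fasting reading from every participant at baseline and at 6 months. Let it, with A1C, decide the glucose part of H1c. The present wording gives a fasting or a post-meal test per person, so some participants would otherwise have no fasting value.
2. Report post-meal glucose descriptively, labelled as glucose after a usual meal.
3. Reconcile the tolerance wording of H1c with the tests described in the two measurement sections.

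**Cost.** All participants must attend fasting, and H1c no longer claims an effect on glucose tolerance. People who entered on the tolerance criterion alone may have a fasting value below the entry band, with little room to fall.

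**If post-meal glucose is to remain a deciding outcome,** use one fixed meal, identical in content and amount, in both arms and at both visits. That costs a standard meal for each test. Keep all randomised participants in the analysis. Dropping readings taken after another meal would be an exclusion made after randomisation that may depend on arm, at odds with the intention-to-treat commitment in Data Analysis.

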Prediabetic individuals 45 years of age and over will be asked to use the PREDIABE-T^R mobile app. The researcher will demonstrate how the application can be downloaded to the participants' phones and how to use it. Before the PREDIABE-T^R app is sent out to the participants, its content will be reviewed for suitability and content validity by health professionals and experts in health communications, informatics, and social media. The mobile app will be used and the process monitored for a period of 6 months. Each week, healthy eating and physical activity messages will be sent over the mobile app and a daily step count will be announced. Education about prediabetes, the risk of diabetes, the calculation of the body mass index, as well as other motivating self-evaluation tools and notifications will be sent out via the PREDIAB-T^R mobile app. The adherence of the experimental group to the intervention will be assessed in the software and encouraging messages will be sent out to ensure continued use of the app. For example: Bracelets inscribed with "Congrats! You've reached your daily steps goal!" or "Keep Active, Keep Protected from Diabetes!" will be distributed as gifts. If requested, the researcher will come to the FHC one day every week to meet with the participants.

The application consists of a total of 3 parts and 4 modules (Figure 2).

- **Module 1: Personal data**

Containing data on the participant's age, gender, telephone number, email and perception of his/her health (bad, so-so, good, very good).

- **Module 2: Medical history of the participant**

In this module, the participants tick the items that apply to themselves or their first-degree relatives by marking the conditions in their medical history that may increase the risk of prediabetes. Additionally, in line with the recommendations of the Turkish Association of Endocrinology and Metabolism, this module contains the Finnish Diabetes Type-2 Risk Score (FINDRISK) which assesses an individual's risk of diabetes (TEMD, 2020).

- **Module 3: Healthy lifestyle behaviors**

The sub-sections of the module are devoted to nutrition, height-weight-body mass index (BMI) and physical activity.

Nutrition

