This study will investigate the efficacy of a mobile application developed under the leadership of public health nursing staff on metabolic factors such as A1C and on physical activity and nutrition. Each message sent to the participants via the app will be evaluated on an individual basis. This strategy will have a potential key role in the development of healthy lifestyle applications in the long term. The control group will be asked to use the Diabetes Checklists and the Turkish Nutrition Guide of the Ministry of Health (Republic of Türkiye, Ministry of Health, Public Health Directorate). The experimental group in the same study will use the PREDIABE-T^R mobile app and the metabolic factors, physical activity levels and Mediterranean diet nutritional behaviors of both groups will be compared. This course of action was planned in the light of current studies (Abbate et al., 2021; Fischer et al., 2016; Ramachandran et al., 2013).

In the development stage of the mobile app, it was designed for use within the healthcare system of the Ministry of Health. Furthermore, it is important that the mobile app will be used for a period of six months, which will provide a time frame to determine the shortcomings of the app. Since the mobile app is free of charge, it can be used on a wide scale by nurses (Abbate et al., 2021). The app can also be considered a facilitating alternative to face-to-face examinations, consultations, and follow-ups over the course of the current pandemic. It therefore opens the door to early diagnosis for individuals with prediabetes. The research is a randomized study of experimental design. The evidential level of the results to be obtained will be high. The developed mobile app will consequently offer individuals with prediabetes, socially disadvantaged groups, and health personnel an instrument that can be conveniently and safely employed. At the end of the study, this mobile application will be integrated into the Google Play Store database.

CONCLUSION

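### The Discussion says the app can be safely employed, but the plan records no harm in either arm that could support this

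*Combined protocol and SAP*

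**What the plan says.** The Discussion says that the trial's evidence will be of a high level and that the app will consequently be "an instrument that can be conveniently and safely employed", for people with prediabetes among others. It then plans release through an app store. The Conclusion adds that administrators and policy-makers will be informed so that use spreads.

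Under Outcome criteria the primary outcome covers change in diet adherence, activity and metabolic measures. The secondary outcome reads: "The secondary outcome is a change in the adults' ability to achieve weight loss". The Data Collection section adds: "Data will be collected on the individuals' sociodemographic features, gender, age, education, profession and medications they are taking", together with a diabetes risk score. Three app usability and usage scales complete the list. Data Analysis names descriptive statistics, group comparisons and an intention-to-treat approach, and says nothing on harms.

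One section is headed Safety. It belongs to the description of the app and reads: "This section contains the data and passwords users will use to access the system".

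On the intervention, the Intervention Group and Physical Activity sections describe an announced daily step count, scheduled weekly activity, gold stars for meeting the requirement and a gift for those who collect enough of them. The Exclusion criteria rule out people who "have any condition that precludes engaging in physical activity".

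**The concern.** The trial encourages more physical activity and weight loss in adults aged 45 to 65. A colleague reading that the resulting app can be used safely would take this as a finding about users. The plan gives no means of reaching such a finding, because it describes no question, form item, outcome or analysis that would register a harm in either arm.

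The efficacy conclusions are untouched. What is at stake is the sentence about safety, which matters because wide release is intended. If the plan is followed as written and the sentence is carried into the report, the absence of recorded harms will follow from not asking and will say nothing about their frequency. Harms not asked about during the trial are hard to recover afterwards.

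**Working it through.** **Step 1. Does any planned item record harm?** Set the statement against each source of data:

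| Source in the plan | Content | Records harm to users? |
|---|---|---|
| Data Collection | Sociodemographics, medications, diabetes risk score | No |
| Primary outcome | Diet adherence screener, activity questionnaire, A1C and glucose | No; metabolic worsening would show, but as efficacy data |
| Secondary outcome | Height, weight, BMI | No; same remark |
| App scales | Usability, intention to continue, loyalty | No |
| Data Analysis | No harm analysis listed | No |
| App section headed Safety | Access data and passwords | No; concerns data security |

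Nothing in the list yields a count of injuries, falls, symptoms during activity or unplanned care.

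**Step 2. The plan's own figures.** The plan gives no figure for harms. Its only relevant numbers are in Sample size determination: effect size 0.666, two-sided 0.05, power 90%, 49 per group, a 10% allowance for losses, and 60 per group enrolled. A two-sample t-test calculation gives 48.36, rounded up to 49, so that figure reproduces. The 49 is the requirement before allowing for losses and is not a forecast of completers. Taking 10% off those enrolled gives 60 × 0.90 = 54 per arm.

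**Step 3. What a clean result could show if harms were asked about.** With zero events among n people, the exact one-sided 95% upper limit for the harm rate is 1 − 0.05^(1/n).

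- n = 60: 1 − 0.05^(1/60) = 0.0487, or 4.9%.
- n = 54: 1 − 0.05^(1/54) = 0.0540, or 5.4%.

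If two-sided 95% exact intervals are reported, 0.05 is replaced by 0.025 and the upper limits become 6.0% (n = 60) and 6.6% (n = 54).

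**Step 4. How likely one arm is to show any event.** The chance of at least one event among 60 is 1 − (1 − p)^60. The documents give no harm rate, so p is assumed:

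- p = 1%: 45%
- p = 2%: 70%
- p = 5%: 95%

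A harm with a true rate of 1% would be missed altogether in an arm of 60 more often than not, even with everyone asked. An unqualified claim of safety is therefore beyond a trial of this size. A bounded statement is within reach, but only if the questions are asked.

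**The case against.** Several objections have force.

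*Safely may not mean freedom from injury.* The sentence also names health personnel as users, the paragraph presents the app as an alternative to face-to-face contact during the pandemic, and the only section headed Safety is about passwords. Data security or remote use are possible readings. The sentence does not say which is meant, so it needs a change of wording on any of them.

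*It is discussion prose.* The hypotheses contain no safety claim, and the Conclusion ties its verdict to effectiveness alone. This stands, and it keeps the point small. Even so, the sentence presents safe use as following from the study.

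*A reader might infer that only app users can report a harm, and that reports would therefore be lopsided.* The documents do not support this. Controls have routine health monitoring at the same health center, and the researcher's measurements carry no restriction by arm. The weekly meeting appears under the app group's heading, but its wording is general: "If requested, the researcher will come to the FHC one day every week to meet with the participants". No section plans to count unprompted reports or compare them by arm, and no reporting rates are given from which to size an imbalance. The only described channel to the researcher between visits that is clearly specific to one arm is the app's message function: "This module will allow users to send direct messages to the researcher, 24/7 for any information they may need". It is offered for information, not as a harm report. The most that follows is a caution against using such messages for a between-arm comparison.

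*A reader might also infer from the exclusion about physical activity that the plan regards activity as hazardous.* The criterion fits simple inability to take part equally well, and no reason is given. The point does not need that inference, since the app's step counts and activity rewards are reason enough to ask.

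**Conclusion.** The point holds in a limited form. The plan describes no collection or analysis of harm in either arm, so the safety statement has no support if it means freedom from harm to users. If data security was meant, this is a matter of wording.

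The size is best put as what the trial could show. As planned, it gives no bound on the harm rate at all. With harms asked about and none reported, the one-sided 95% upper limit is 4.9% for 60 per arm and about 5.4% for 54. These limits assume that every person counted is asked and answers accurately, and that losses come to the planned 10%.

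This is a cheap improvement. Sample size, randomization and the efficacy analyses are unaffected.

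**What to change.** 1. At the six-month assessment already planned, ask both arms the same short closed set of questions: injury or fall during activity, symptoms during activity, and unplanned health-care contact since baseline.
2. Add one sentence to Data Analysis: counts and proportions by arm, with exact confidence intervals, reported descriptively. Keep unprompted app messages out of any between-arm comparison.
3. Limit the Discussion sentence to what was observed, with its upper limit. If data security was meant, say that instead.
4. If the questions are not added, delete the word safely.

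The cost is a few questions, one table and a changed sentence. There are drawbacks to state openly. Recall over six months will miss minor events. The researchers are not blinded, so identical closed wording reduces differential questioning but cannot remove it. The resulting safety statement will also be weaker than the present one.
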